Aim 2: To determine accuracy of the ratio of PIGF/sFlt-1 in predicting PET and the effect of metformin on this ratio

The objectives under this aim will include,

1. A comparison of the serum levels of the PIGF/sFlt-1 ratio measured in early pregnancy between non-PET and PET patients.
2. A comparison of the PIGF/sFlt-1 ratio PET in patients who received metformin versus standard care group.

Aim 3: To study the molecular mechanisms and signaling pathways associated with increased levels of sFlt-1 and PET.

Regarding aim 3: in response to the reviewer's comments, the study team has agreed to collect the blood sample and placenta from the patients and store them for future analysis.

4. Preliminary data or studies

Metformin safety in pregnancy

substantial evidence on the benefits of metformin an antihyperglycemic agent when pregnant women with gestational and Type 2 diabetes. In polycystic ovary syndrome

1 Jan - Revised On May 2017

Page 5 of 22

(PCOS) patients, it is known to decrease the risk of first trimester miscarriages and the incidence of gestational diabetes (48,49). In diabetic pregnancies, metformin has been associated with favorable maternal and neonatal outcomes (50,51). Observed maternal outcomes include less weight gain during pregnancy, better glycemic control, and reduced fat distribution (52). Other benefits include a reduction in pregnancy induced hypertension and PET, lower risk of neonatal hypoglycemia and ICU admission. Neonatal outcomes include: reduced fat around organs, which could result in improved insulin resistance and prevention of diabetes later in life (52). Even though metformin is known to cross the placenta, its use in early pregnancy or late pregnancy has not been shown to be associated with an increased risk of congenital malformation or adverse neonatal outcomes except a lower neonatal birth weight (53–56).

Metformin has been safely administered at the dose we propose to use here to diabetic patients. It has become the first line treatment of type 2 DM in pregnancy and poorly controlled gestational diabetes on diet based on the NICE guideline and the national diabetes guideline in Qatar. However, anticipated side effects include: GI disturbances such as gas (4-12%), heartburn, stomach pain (3-4%), nausea (7-9%), and GI changes. Serious side effects associated with its use are hypoglycemia and lactic acidosis which are extremely rare (<1%) (57).

Metformin in PET:

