- (c) At delivery data to be collected will include gestational age at admission, vital signs, indication for delivery, type of delivery, compliance with protocol, blood for CBC, LFT, and the biomarkers of interest. Post-delivery, discharge vitals, antihypertensive treatment on discharge will be collected.

(d) Exit interview: patient will be called to check for any relevant ADR.

8. Data Management and Analysis plan

Data management:

Upon randomization, research coordinators will be responsible for data collection using approved CRFs. To maintain patient confidentiality, study document such as signed informed consent, and CRFs will be stored in locked cabinets, excel file containing patient identifiable information will be password protected, and all data including patient clinical information and research laboratory results will be entered into the clinical trial management software using patient generated study ID number.

Data analysis:

Descriptive data: Numerical data will be presented as mean and standard deviation where normally distributed or median and range where it's not normally distributed. Categorical data will be presented as frequency and percentages. The percentage of women developed PET will be compared between the intervention and control group using chi square test.

Quantitative data between two arms will be analyzed using either "Unpaired t test or Mann Whitney U test depending on normality of the data distribution". Also, outcomes measured at different time points should be statistically analyzed both within and between groups using repeated measure ANOVA statistical method followed by appropriate multiple comparison tests. All P values presented will be two-tailed. A multivariate logistic regression will be employed to assess the association between metformin use and PET adjusting for confounding factors such as patient demographics (age, GA at delivery, history of risk factors of PET\mentioned above) and co-morbidities such as DM, the dose of metformin, the need to use of antihypertensive drugs, including duration of treatment and any other medications. P values <0.05 will be considered as statistically significant. All Statistical analyses will be done using statistical packages SPSS 22.0 (SPSS Inc. Chicago, IL) and Epi-info (Centers for Disease Control and Prevention, Atlanta, GA) software.

9. Anticipated results and evaluation criteria

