As an open label study, we hope the results of this study will generate robust data that will be used to inform the design equipped to design of a larger national study. Moreover, based on the findings of previous published literature, we predict that expression of sFlt-1, VEGF and PIGF will be significantly altered in pre-eclamptic patients. The design of this study will help determine and validate the clinical utility of the aforementioned biomarker in routine practice for the prediction of PET and disease severity. The use of metformin is expected to reduce the anticipated effects of sFlt-1 as an antiangiogenic factor, therefore, reducing the incidence of

PET and indeed improving maternal and neonatal outcomes and quality of life, reducing hospital admissions and cost of care and better utilization of health care system resources.

This collaborative study involves investigators (scientists and clinicians) from the PHCC, HGH, Women's Hospital [name] and Sidra. Such a cross-disciplinary approach will provide an opportunity for training future scientist in the field of women's health. The more junior members of the team will have the opportunity to be trained on translational research design, and clinical trial management and thereby enhancing the research capacity which both are aligned with Qatar national health strategy. The women hospital will be better catered with enhanced research skills. Pregnant women are usually excluded from clinical trial; however, an advantage of this trial is the safety the intervention (metformin) and thereby increasing public engagement with research and awareness of its importance and benefits.

Evaluation criteria for this study are patient recruitment, quality and consistency of the data and safety of the intervention. Further, the percentage women who developed PET in each arm as well as changes in the studied biomarkers will be quantified and accepting the null hypothesis.

10. Plans for disseminating research results

Once the project is funded, the study team will initiate monthly meetings to discuss study plans and patient recruitment. Team leaders will also meet monthly to share study updates. Furthermore, the study results will be shared among peers in the department through presentation of study findings. Finally, once the study is completed we aim to present our finding at the [name] Medical Corporation Annual Research Day, local and international conferences and in peer-reviewed journals.

11. Future plans

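### Aim 2 promises the predictive accuracy of the PlGF/sFlt-1 ratio, but the plan specifies only a comparison of levels and no measure of accuracy

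*SAP*

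**What the plan says.** All references are to the SAP.

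- **Sections 2 and 3, Aim 2:** "To determine accuracy of the ratio of PIGF/sFlt-1 in predicting PET and the effect of metformin on this ratio". The aim has two parts, accuracy and the effect of metformin.
- **Section 3, Aim 2, objective 1** (the accuracy part): "A comparison of the serum levels of the PIGF/sFlt-1 ratio measured in early pregnancy between non-PET and PET patients". It does not mention treatment arm.
- **Section 3, Aim 2, objective 2** (the metformin part): "A comparison of the PIGF/sFlt-1 ratio PET in patients who received metformin versus standard care group".
- **Section 8, Data analysis:** continuous data are covered by a sentence that begins "Quantitative data between two arms will be analyzed using either" and continues "Unpaired t test or Mann Whitney U test depending on normality of the data distribution". For serial data, "outcomes measured at different time points should be statistically analyzed both within and between groups using repeated measure ANOVA statistical method". The regression is described as follows: "A multivariate logistic regression will be employed to assess the association between metformin use and PET adjusting for confounding factors". The adjustment factors listed after it do not name the ratio.
- **Section 9:** the design is expected to "help determine and validate the clinical utility of the aforementioned biomarker in routine practice for the prediction of PET", and to do the same for disease severity.

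No ROC curve, AUC, sensitivity, specificity, predictive value or cut-off is planned for the ratio anywhere in the SAP. The background does use that scale for other tools: it faults current prediction criteria for lack of specificity and uterine artery Doppler for poor sensitivity.

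**The concern.** Accuracy describes how well a marker separates individual women who will develop PET from those who will not. A test of mean or median levels asks only whether the two distributions differ at all. With a few hundred women, a difference too small to be useful for prediction can still be statistically significant.

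The aim, the objective and the promised conclusion therefore do not fit together. If the plan is followed as written, the accuracy question in Aim 2 has no planned estimate, and the clinical-utility statement in Section 9 would have only a p-value behind it. If an accuracy measure were added later, the measure and its cut-off could be chosen after seeing the data. Choosing the statistic that answers a stated aim belongs in the analysis plan, so this is not a detail that an SAP would normally leave to the protocol.

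**Working it through.** **Inputs from Section 6:** PET 11.3% in controls and 3% on metformin; 80% power; 5% significance; 172 evaluable women per arm at 1:1. Section 8 makes all p-values two-tailed. The SAP gives no sample-size figure for Aim 2 and no means, SDs or cut-off for the ratio.

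**Reproducing the SAP's 172 per arm.**
- Mean proportion = (0.113 + 0.03)/2 = 0.0715.
- Uncorrected n = [1.96 x sqrt(2 x 0.0715 x 0.9285) + 0.8416 x sqrt(0.113 x 0.887 + 0.03 x 0.97)]^2 / 0.083^2 = (0.7142 + 0.3027)^2 / 0.006889 = 150.1.
- With continuity correction: (150.1/4) x [1 + sqrt(1 + 4/(150.1 x 0.083))]^2 = 173.4, so 174 per arm, within two of the stated 172.

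**Expected cases.** 172 x 0.113 = 19.4 and 172 x 0.03 = 5.2, total 24.6. That is about 25 PET and 344 - 25 = 319 non-PET women.

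**AUC at which a Mann-Whitney test just reaches p = 0.05.**
- Null SE of the AUC = sqrt[(25 + 319 + 1)/(12 x 25 x 319)] = sqrt(345/95,700) = 0.060.
- 0.5 + 1.96 x 0.060 = **0.62**.
- The allocation text is inconsistent (1:2 under randomization in Section 5, 1:1 in Section 6), so I varied it. With 414 women at 1:1 there are about 30 cases and the threshold AUC is 0.61. With 414 women at 1:2, in either direction, there are 24 to 35 cases and the threshold is 0.62 to 0.60. The result barely moves.

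**Illustration under an assumed equal-variance normal model.** Let d be the difference in SD units.
- t = d x sqrt(25 x 319/344) = 4.815d
- AUC = Phi(d/sqrt 2)
- Sensitivity at a 10% false-positive rate = Phi(d - 1.2816)

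| d (assumed) | t | p | AUC | Sensitivity |
|---|---|---|---|---|
| 0.41 | 1.96 | 0.05 | 0.61 | 19% |
| 0.6 | 2.89 | 0.004 | 0.66 | 25% |
| 0.8 | 3.85 | 0.0001 | 0.71 | 32% |
| 1.5 | 7.22 | <0.0001 | 0.86 | 59% |

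At d = 0.6, with prevalence 25/344 = 7.3%, the positive predictive value is 0.248 x 0.073 / (0.248 x 0.073 + 0.10 x 0.927) = 16%.

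**Precision available (Hanley-McNeil).** SE^2 = [A(1 - A) + (n1 - 1)(Q1 - A^2) + (n0 - 1)(Q2 - A^2)]/(n1 n0), with Q1 = A/(2 - A) and Q2 = 2A^2/(1 + A).
- A = 0.664, 25 and 319 women: (0.223 + 24 x 0.056 + 318 x 0.089)/7,975 = 0.00375, SE 0.061, half-width **0.12**.
- Assumed AUC 0.75: 95% CI 0.64 to 0.86 with all women, 0.62 to 0.88 in the control arm alone (19 cases of 172).
- An observed sensitivity of 70% in 25 cases would have a 95% CI of about 50% to 84%.

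**Does ignoring arm distort the AUC?** Suppose the baseline ratio is unaffected by treatment and metformin prevents the same share of PET at every level of the ratio. Prevented cases (11.3% - 3% = 8.3% of the metformin arm) then sit among the non-cases and make up 0.083/(0.887 + 0.97) = 4.5% of them. At d = 0.6 the pooled AUC = 0.955 x 0.664 + 0.045 x 0.5 = 0.657, against 0.664 in controls. At d = 0.8 it is 0.705 against 0.714. The shift is about 0.01.

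**The case against.** Several objections are fair.

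- **The Mann-Whitney statistic can be rescaled.** U divided by the product of the two group sizes is the AUC, so that test would be one step from an accuracy estimate. This is true. However, Section 8 assigns the test to comparisons between arms, substitutes a t test if the data look normal, and plans neither the rescaling nor an interval.
- **A reader might infer that the SAP assigns a wrong test to PET versus non-PET.** It does not. The t test or Mann-Whitney sentence is limited to the two arms, and no test is named for objective 1. The fault is that no analysis is specified for the accuracy part of Aim 2.
- **A reader might infer that the comparison is pooled over arms and seriously biased as a result.** Pooling is a natural reading of objective 1 but is not stated. Under a constant relative risk it moves the AUC by about 0.01, far less than the half-width of 0.12. It would matter more if the effect of metformin varied with the ratio, and the documents give no figures on that.
- **A reader might infer that the control arm should give the main estimate because metformin does not touch it.** Section 5 (randomization and initiation) moves controls who start metformin for gestational diabetes into the intervention group for analysis. Controls as randomised therefore include metformin users, and controls as analysed are selected on a later event. Restricting to controls also cuts the cases to about 19 and widens the half-width at an AUC of 0.66 to about 0.14.
- **Section 9 states anticipated results, and the trial is described as preparing a larger one.** This lowers the stakes but does not supply a statistic for Aim 2. The SAP also contains no rule that p < 0.05 will be read as proof of prediction; that is a risk, not a stated plan.

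**Conclusion.** The point holds in this form: the SAP states an accuracy aim and promises validation for routine prediction, but specifies only a comparison of levels and no accuracy measure. With about 25 cases and 319 non-cases, significance is compatible with an AUC of about 0.62.

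The case count rests on the SAP's planning rates and 1:1 allocation. The sensitivities, and the AUC values for a given d, rest on an assumed normal model and chosen differences. The calculation does not show that the ratio will predict poorly: a 1.5 SD difference would give an AUC of 0.86. It shows that the planned comparison cannot tell these situations apart on the scale that the aim requires.

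Objective 2 does serve the metformin part of Aim 2, and the Aim 1 comparison of PET incidence is unaffected. The SAP should be corrected, but the main comparison of the trial is not at risk.

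**What to change.** **Section 8.** For the accuracy part of Aim 2, replace the comparison of levels with:
- the AUC and 95% CI of the baseline PlGF/sFlt-1 ratio (11+0 to 13+6 weeks), using all women as randomised and stratified by arm;
- sensitivity with its CI at one false-positive rate fixed before analysis (the 10% used above is only an illustration);
- if wanted, control-arm results as a sensitivity analysis.

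State that the baseline sample used is drawn before the first metformin dose. The SAP gives the same gestational window for baseline data and start of treatment, so this order is implied but not written. The comparison of levels can stay as a descriptive result.

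**Section 9.** Replace the promise to determine and validate clinical utility with one to estimate predictive accuracy.

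**Cost.** Some SAP wording and one short analysis of data already collected, with no change to sample size or procedures. The downside is a more modest claim: with about 25 events the AUC is known only to within about 0.12 either way.

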each visit or telephone call. Furthermore, to increase patient medication adherence, a reminder SMS will be send as well as three telephone calls to individual patient on regular basis. Adverse drug reaction (ADRs) will be reported using [name] Medical Corporation ADR form (Appendix 7) to both DSMC and MRC when they occur, however, serious ADRs will be reported within 48 hours by the study PI.

6. Sample size and calculation

Our sample size calculation was based on Syngelaki A. et al. (2016) findings. In this study, obese patient where either randomized to metformin or placebo to see the effect on neonatal birth weight. As a secondary outcome, metformin use was associated with 76% reduction in PET (3% versus 11.3% respectively, OR 0.24, 95% CI 0.10 – 0.61, $P = 0.001$).

We expect that for a study power of 80% and to detect a reduction at a level of 5% significance, with considering above outcome estimates it is approximately estimated to be 172 patients in each arm, for a total of 344 in both group based on 1:1 ratio. Allowing for a maximum 20% dropout, we estimate that 414 patients would need to undergo randomization, to give 207 patients in each group.

7. Data collection methods and procedure

These will be at baseline, in the second and again in the third trimesters. The data to be collected include patient clinical information, blood sample and placental tissue (appendix 5). At each study visit 5 ml maternal venous whole blood will be collected by a laboratory phlebotomist or a nurse (one at baseline, and one at each following trimester/visit and admission/s, see appendix 2) for all included subjects. The blood sample will be used for measuring blood markers for aim 2 and stored for future DNA/RNA analysis for aim 3. In addition, placental tissue will be collected and stored for future DNA/RNA analysis. In brief:

- (a) Baseline Data (Week 11⁺⁰ to 13⁺⁶): Patient sociodemographic data including age and ethnicity, Obstetrical, medical, surgical and medication history, current pregnancy information, CBC, as routinely done and study biomarkers of LFT, serum creatinine, sFlt-1, VEGF and PIGF.
- (b) Second (week 19⁺⁰ to 24⁺⁶) and third trimester visits (week 32⁺⁰ to 34⁺⁶): At these visits the same data collected at baseline will be obtained. If the patient is, however, admitted for pre-eclampsia before the third visit, the collection will follow the pre-eclampsia diagnosis at admission including treatment offered, length of hospitalization and management.

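### The PlGF/sFlt-1 ratio is analysed without gestational age at the blood draw, although draws under one visit label span three to six weeks

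*SAP*

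**What the plan says.** Section 3 sets two comparisons of the ratio under Aim 2. Objective 1 is "A comparison of the serum levels of the PIGF/sFlt-1 ratio measured in early pregnancy between non-PET and PET patients". Objective 2 is "A comparison of the PIGF/sFlt-1 ratio PET in patients who received metformin versus standard care group". Neither names a covariate, and objective 1 does not say which visit counts as early pregnancy.

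Section 7 gives the draw windows: "Baseline Data (Week 11⁺⁰ to 13⁺⁶" and "Second (week 19⁺⁰ to 24⁺⁶) and third trimester visits (week 32⁺⁰ to 34⁺⁶". Blood is also taken outside these windows: "one at baseline, and one at each following trimester/visit and admission/s, see appendix 2". For women who develop PET early, the timing changes: "If the patient is, however, admitted for pre-eclampsia before the third visit, the collection will follow the pre-eclampsia diagnosis at admission".

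Section 8 gives the tests. Quantitative data between arms get an "Unpaired t test or Mann Whitney U test depending on normality of the data distribution". For serial data, "outcomes measured at different time points should be statistically analyzed both within and between groups using repeated measure ANOVA statistical method". The only adjusted model is a logistic regression of PET on metformin use. It does not contain the ratio, and its only gestational-age term is gestational age at delivery.

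**The concern.** All samples with the same visit label are analysed as if drawn at the same gestation. At the second visit, two such samples can be almost six weeks apart. If the ratio moves with gestation, that spread has two possible effects.

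- **Objective 1.** PET status is not randomised. If women who later develop PET tend to be sampled earlier or later in the window, the timing difference enters the ratio difference directly and could be read as predictive value. Section 9 expects this design to help establish the marker's clinical usefulness for prediction, so the comparison carries weight.
- **Objective 2.** Between randomised arms at scheduled visits, timing balances on average. The spread then only adds noise, most of it in the 6-week window.

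Gestational age at each draw follows from the pregnancy dating on which eligibility and the visit windows already depend, together with the date of the draw. Leaving it out of the analysis gains nothing.

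**Working it through.** **The plan's own figure.** The SAP gives no sample size for the ratio. Its only calculation (Section 6) is for PET incidence: 11.3% versus 3%, two-sided 5%, 80% power, 172 per arm. The standard two-proportion formula gives 151 per arm without continuity correction and 174 with it, so 172 is reproduced to within about 1%. I use it only to estimate the number of PET cases.

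**Window widths (Section 7).** 11+0 to 13+6 is 21 days; 19+0 to 24+6 is 42 days; 32+0 to 34+6 is 21 days.

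**Spread of gestation at the draw**, assuming draws uniform over a window of d days: SD = √((d² − 1)/12)/7.
- 21 days: √(440/12)/7 = 0.87 weeks.
- 42 days: √(1763/12)/7 = 1.73 weeks.

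**Precision.** Let b be the slope of the log ratio in residual SDs per week. The SAP gives none, so b = 0.1 to 0.4 is an assumption. Variance inflation is V = 1 + (b × SD)², and the share of variance due to gestation is (b × SD)²/V. A comparison with 80% power when adjusted has power Φ(2.80/√V − 1.96) when unadjusted.

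| b (SD/week) | Share, baseline | Share, visit 2 | Power, baseline | Power, visit 2 |
|---|---|---|---|---|
| 0.1 | 0.7% | 2.9% | 79.7% | 78.8% |
| 0.2 | 2.9% | 10.7% | 78.8% | 75.4% |
| 0.3 | 6.3% | 21.3% | 77.4% | 70.1% |
| 0.4 | 10.7% | 32.4% | 75.4% | 63.4% |

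At b = 0.05 the loss is negligible (79.9% and 79.7%).

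**Bias in objective 1.** Expected PET cases are 172 × 0.113 + 172 × 0.03 = 19.4 + 5.2 = 24.6, so about 25 against 319 non-cases. The standard error of the standardised difference is √(1/25 + 1/319) = 0.208, and the difference detectable with 80% power is 2.80 × 0.208 = 0.58 SD.

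Suppose mean draw time differs systematically by δ weeks between PET and non-PET women (also an assumption). The spurious difference is b × δ. With λ = bδ/(0.208 × √V), the rejection rate when the ratio has no predictive value is Φ(λ − 1.96) + Φ(−λ − 1.96).

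| b (SD/week) | Spurious difference, δ = 0.5 | Error rate, δ = 0.5 | Error rate, δ = 1 |
|---|---|---|---|
| 0.1 | 0.05 SD | 5.7% | 7.7% |
| 0.2 | 0.10 SD | 7.6% | 15.8% |
| 0.3 | 0.15 SD | 10.8% | 28.8% |
| 0.4 | 0.20 SD | 14.9% | 44.4% |

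At δ = 0.5 the spurious difference is 9% to 34% of the detectable 0.58 SD. With no systematic timing difference, chance alone gives a difference with SD 0.87 × 0.208 = 0.18 weeks. The standard error already reflects this, and the error rate stays at 5%.

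**The case against.** The strongest case against is that both quantities driving the size are assumed. The SAP reports no weekly slope, direction or SD for the ratio. It also gives no reason to expect PET and non-PET women to be sampled at different times: every participant is high risk by inclusion, is screened before about 12 weeks, and has baseline data collected in the same three-week window. PET as defined in Section 5 arises after 20 weeks, so baseline timing cannot respond to the outcome. A half-week difference is about 2.8 times the chance SD (0.5/0.18) and would need a systematic cause, such as earlier booking of the women at greatest risk, which is conjecture. All of this stands. It is why the bias is stated as conditional, and why the likely cost in objective 1 is a small loss of precision.

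A reader might infer that timing could pass for a metformin effect on the ratio. The documents do not support that for the as-randomised comparison at scheduled visits: randomisation balances timing on average, and Section 5 specifies intention to treat. Objective 2 is worded by treatment received, Section 5 moves some controls to the intervention group, and collection can follow a PET admission. Each of these could disturb the balance, but they are separate problems, and a gestational-age covariate would not by itself cure them.

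A reader might also carry the 6-week figures over to objective 1. Early pregnancy most naturally means the baseline draw, with its 3-week window. The 42-day window bears mainly on objective 2.

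**Conclusion.** The point holds as an improvement to the analysis. Section 8 fixes unadjusted tests for a marker drawn over windows of 21, 42 and 21 days, and nowhere uses gestational age at the draw. If the ratio changes with gestation:

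- Objective 1 could be confounded to the extent that draw timing differs by PET status: an error rate of about 6-15% instead of 5% for an assumed half-week difference and slopes of 0.1 to 0.4 SD per week. Without a systematic difference the rate is 5%, and the cost is 1-11% of the variance at baseline.
- Objective 2, as randomised and at scheduled visits, loses precision only: 3-32% of the variance at the second visit under the same slopes.

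These ranges rest on assumed slopes, uniform draws and the case count implied by Section 6. The documents do not show that any timing difference exists, or that an Aim 2 result would be spurious. The PET incidence comparison is unaffected.

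**What to change.** In Section 8, state that log sFlt-1, PlGF, VEGF and the ratio at scheduled visits are analysed with exact gestational age at the draw, in days, as a covariate (linear plus a quadratic term or a spline). Alternatively, convert each value first to a gestation-adjusted residual or a multiple of the median. Apply this to both Aim 2 objectives, and say that objective 1 uses the baseline draw if that is what is meant. Keep samples taken at a PET admission separate from scheduled-visit samples, because their timing is set by the outcome.

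The cost is one or two degrees of freedom and a little analysis work, with no new data. If the true slope is zero, nothing is gained and almost nothing is lost. Fixing the rule before analysis also removes a later choice between adjusted and unadjusted results.
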